4.3 Withdrawal of Subjects from Study

Subjects **must be withdrawn from the trial** (treatment and procedures) for the following reasons:

- Subject withdraws consent from study treatment and study procedures. A subject must be removed from the trial at his/her own request or at the request of his/her legally acceptable representative. At any time during the trial and without giving reasons, a subject may decline to participate further. The subject will not suffer any disadvantage as a result.
- Pregnancy. Pregnancies will be reported to Taiho within 24 hours of having knowledge of the event. Pregnancy will not be reported as an SAE but the subject must be withdrawn from the trial immediately. (Note: subjects who have been withdrawn from treatment with study drug because of pregnancy should not undergo CT scans [with contrast]/MRI or bone scans while pregnant.)
- If, in the investigator's opinion, continuation of the trial would be harmful to the subject's well-being.
- Subject is lost to follow-up.
- Death.

All subjects who discontinue should comply with protocol specified follow-up and survival procedures. The ONLY exception to this requirement is when a subject withdraws consent for all

study procedures or loses the ability to consent freely (i.e., is imprisoned or involuntarily incarcerated for the treatment of either a psychiatric or physical illness). If a subject was withdrawn before completing the study, the reason for withdrawal must be entered on the appropriate case report form page.

Subjects **may be** withdrawn from study treatment for the following reasons:

- The subject is non-compliant with TAS 102 administration, ramucirumab administration, or trial procedures; including the use of anti-cancer therapy not prescribed by the study protocol.
- Severe allergic reaction to TAS 102 or ramucirumab.
- The development of a second cancer.
- Development of an illness or situation which would, in the judgment of the investigator, significantly affect assessments of clinical status and trial endpoints.
- Deterioration of ECOG performance status to 3 or 4.
- Use of illicit drugs or other substances that may, in the opinion of the investigator, have a reasonable chance of contributing to toxicity or otherwise skewing trial result.

Any subject removed from the trial will remain under medical supervision until discharge or transfer is medically acceptable.

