Any subject with progression of disease will come off of treatment except for patients deriving clinical benefit as deemed by the principal investigator with a maximum of 24 months on therapy. In all cases, the reason for withdrawal must be recorded in the CRF and in the subject's medical records.

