4.3.2 Patient Replacement

Dropout (see 4.3.1 for definition of "dropout") patients will need to be replaced.

Patients will be replaced if they come off treatment without any response evaluation for reasons other than drug related AE or disease progression.

5. Treatment Plan

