If a subject experiences a clinically significant and/or unacceptable toxicity, dosing will be interrupted and supportive therapy administered as required.

5.1.1.1 Management for Treatment-Related Toxicity of TAS 102

5.1.1.1.1 Non-hematologic toxicities of TAS 102

Table 3. Non-hematologic toxicity management

Grade¶	Dose hold/resumption within a 28-day treatment cycle	Dose adjustment for next cycle
Grade 1 or 2		
Any occurrence	Maintain treatment at the same dose level	None
Grade 3* or higher		
1 st , 2 nd or 3 rd occurrence	Suspend treatment until Grade 0 or 1	Reduce by 1 dose level from the previous level
4 th occurrence	Discontinue treatment	Discontinue treatment

¶ At the discretion of the investigator, patients may continue on study medication at the same dose without reduction or interruption for AEs (irrespective of grade) considered unlikely to become serious or life-threatening (including, but not limited to, fatigue, alopecia, changes in libido, and dry skin).

* Except for grade 3 nausea and/or vomiting controlled by antiemetic therapy or diarrhea responsive to antidiarrheal medication. Moreover, if grade 4 non-hematotoxicity that is related to the protocol therapy is observed, protocol therapy is to be discontinued. However, in case of adverse events, which can clearly be judged to have derived from the primary disease, depending on the judgement of the investigator (subinvestigator) protocol therapy can be continued. In this case, the reason for this judgement must be recorded in the medical records, etc. (For example: Grade 3 cancer pain that is associated with the primary disease, Grade 3 weight loss that is associated with the primary disease, etc.)

5.1.1.1.2 Hematologic toxicities of TAS 102

Criteria for dose hold and resumption in response to hematologic toxicities related to myelosuppression are described in Table 2.

Uncomplicated neutropenia or thrombocytopenia \leq grade 3 does not require a reduction in dose of study medication. Patients who experience uncomplicated Grade 4 neutropenia or thrombocytopenia that results in a >1 week delay of the start of the next cycle should start the next cycle with dose reduction in $5\text{mg}/\text{m}^2$ step. If toxicity remains despite 4 dose reductions or at a minimum dose ($15\text{mg}/\text{m}^2$ twice a day), discontinue TAS 102.

Table 4. Hematologic toxicity management

Parameter	Hold Criteria		Resumption Criteria*	Dose adjustment for next cycle
	Conventional Units	SI units		

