5.1.1.2.2 Hypertension

- If patients develop hypertension during the study, they should be treated with antihypertensive medications according to standard medical practice.
- The following are treatment guidelines for ramucirumab related hypertension

Grade	Management
Grade 1 or 2	
 If the hypertension is not associated with symptoms, continue ramucirumab and initiate antihypertensive therapy If the hypertension is associated with symptoms, hold ramucirumab until symptoms resolve and initiate antihypertensive therapy
Grade 3	
 For Grade 3 hypertension not associated with symptoms, continue ramucirumab with more intensive antihypertensive therapy. If systolic BP remains ≥ 160 mm Hg or diastolic BP ≥ 100 mm Hg > 2 weeks after initiation of additional antihypertensive therapy, hold ramucirumab while continuing appropriate antihypertensive therapy If the hypertension is associated with symptoms, hold ramucirumab until symptoms resolve and initiate

	antihypertensive therapy
Grade 4	
 ○ Patients with Grade 4 hypertension (life-threatening consequences, eg, malignant hypertension, transient or permanent neurologic deficit, hypertensive crisis; or urgent intervention indicated) or patients whose hypertension is poorly controlled (> 160 mm Hg systolic or > 100 mm Hg diastolic for > 4 weeks) despite (> 2 oral agents at MTD) will be discontinued from study therapy.

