5.1.1.2.3 Thromboembolic events

- Investigators should perform all testing required to fully characterize arterial or venous thrombotic/vascular events.
- Ramucirumab should be discontinued in the event of any Grade 3-4 arterial thromboembolic event or any Grade 3-4 venous thromboembolic event that is considered by the investigator to be life-threatening, or symptomatic and not adequately treated by anticoagulation therapy.
- At the investigator's discretion, ramucirumab may be continued in this setting of an incidentally diagnosed asymptomatic deep vein thrombosis or pulmonary embolism, or following a symptomatic deep vein thrombosis or pulmonary embolism when symptoms have resolved with the institution of anticoagulation therapy.
- In the event that a patient experiences a Grade 4 pulmonary embolism or a Grade 3-4 venous thromboembolic event that is considered by the investigator to be life-threatening, or symptomatic and not adequately treated by anticoagulation therapy, the patient will not receive further ramucirumab and be discontinued from study therapy.
- Ramucirumab should also be discontinued, and a patient will be discontinued from study therapy in the setting of a deep vein thrombosis or pulmonary embolism that occurs or intensifies while the patient is receiving therapeutic anticoagulation therapy.

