9.2 Determination of sample size

The primary objective of this study is overall survival at 6 months. Overall survival (OS) will be defined as the time from starting on trial to date of death due to any cause. Dropouts/screen failures defined in section 4.3.1. Patients will be considered inevaluable for the primary endpoint of 6 months of overall survival if they are not able to complete first cycle or if they are lost follow-up prior to 6 months from starting on trial except death. Inevaluable patients will be replaced. The study will test the null hypothesis of $\leq 45\%$ of OS at 6 month against the alternative of $\geq 70\%$ of OS at 6 month. The sample size was determined based on the Simon's two-stage minimax design. With one-sided 10% of type I error rate and 90% power, a sample of evaluable 25 patients will be evaluated; 15 in first stage and additional 10 patients in second stage. If 7 or more out of 15 survive 6 months or more, the study goes on the second stage. The experimental treatment will be deemed to have good activity if ≥ 15 out of 25 patients survive 6 months or more. We will continue to recruit patients during interim analysis

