APPENDIX A: RECIST Criteria for Measuring Tumor Response Antitumor Effect

Response and progression will be evaluated in this study using the new international criteria proposed by the revised Response Evaluation Criteria in Solid Tumors (RECIST) guideline (version 1.1) (Eisenhauer et al., 2009). Changes in the largest diameter (unidimensional measurement) of the tumor lesions and the shortest diameter in the case of malignant lymph nodes are used in the RECIST criteria.

Definitions

Evaluable for toxicity. All patients will be evaluable for toxicity from the time of their first treatment with ramucirumab or TAS 102.

Evaluable for objective response. Only those patients who have measurable disease present at baseline, have received at least one cycle of therapy, and have had their disease re-evaluated

will be considered evaluable for response. These patients will have their response classified according to the definitions stated below. (Note: Patients who exhibit objective disease progression prior to the end of cycle 1 will also be considered evaluable.)

Disease Parameters

Measurable disease. Measurable lesions are defined as those that can be accurately measured in at least one dimension (longest diameter to be recorded) as ≥ 10 mm with CT scan, MRI or calipers by clinical exam. All tumor measurements must be recorded in millimeters (or decimal fractions of centimeters).

Note: Tumor lesions that are situated in a previously irradiated area might be considered measurable if the lesion has increased in size since the radiation.

Malignant lymph nodes. To be considered pathologically enlarged and measurable, a lymph node must be ≥ 15 mm in short axis when assessed by CT scan (CT scan slice thickness recommended to be no greater than 5 mm). At baseline and in follow-up, only the short axis will be measured and followed.

Non-measurable disease. All other lesions (or sites of disease), including small lesions (longest diameter < 10 mm or pathological lymph nodes with ≥ 10 to < 15 mm short axis), are considered non-measurable disease. Bone lesions, leptomeningeal disease, ascites, pleural/pericardial effusions, lymphangitis cutis/pulmonitis, and abdominal masses (not followed by CT or MRI), are considered as non-measurable.

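### Section 9.2 drops patients who stop in cycle 1 for toxicity or progression, and live past it, from the 7/15 and 15/25 survival counts, out of line with 4.3.1 and 4.3.2

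*Combined protocol and SAP*

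**What the plan says.** Section 9.2 defines OS from starting on trial to death from any cause. It then sets who counts: "Patients will be considered inevaluable for the primary endpoint of 6 months of overall survival if they are not able to complete first cycle". Loss to follow-up before 6 months is a second ground in the same sentence. An exception for death closes that sentence, and inevaluable patients are replaced. Completing the first cycle is not defined. Section 9.3 applies the final threshold of 15 survivors to 25 evaluable patients, so this clause fixes the denominator of the primary decision.

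Section 4.3.2 words replacement differently: "Patients will be replaced if they come off treatment without any response evaluation for reasons other than drug related AE or disease progression". Section 4.3.1 leaves death, progression and severe toxicity out of its dropout definition, but its last sentence permits replacement of anyone who withdraws from treatment, whatever the reason.

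Appendix A, on response, says "Patients who exhibit objective disease progression prior to the end of cycle 1 will also be considered evaluable".

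Several rules can end treatment within cycle 1:
- Section 5.1.1.1.1: "Moreover, if grade 4 non-hematotoxicity that is related to the protocol therapy is observed, protocol therapy is to be discontinued".
- Section 5.1.1.2.2, grade 4 hypertension: such patients "will be discontinued from study therapy".
- Section 5.1.1.2.3, certain venous thromboembolic events: "the patient will not receive further ramucirumab and be discontinued from study therapy".
- Section 4.3: "Any subject with progression of disease will come off of treatment except for patients deriving clinical benefit".

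Section 4.3 also says "All subjects who discontinue should comply with protocol specified follow-up and survival procedures".

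**The concern.** Toxicity or progression that stops treatment in the first 28 days is an outcome of the regimen. Survival, unlike response, needs no completed cycle to be assessed. Under 9.2 a patient stopped in cycle 1 by a drug reaction who dies in month 3 is replaced by someone new. The 7/15 and 15/25 counts then no longer describe everyone who started, although the primary objective is 6-month OS in patients receiving the combination. If those removed survive worse than those who stay, the counts are biased upward.

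The sections also give staff no single rule. A cycle 1 stop for a drug-related event is replaced under 9.2, is outside the replacement rule of 4.3.2, and may be replaced under the last sentence of 4.3.1. A patient with measurable disease who comes off treatment for objective progression in cycle 1 counts for response but not for the primary endpoint.

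**Working it through.** **Inputs from the plan (synopsis, 9.2, 9.3).** Null 6-month OS 0.45, alternative 0.70, one-sided type I error 10%, power 90%; continue if at least 7 of 15 survive, success if at least 15 of 25.

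**Inputs not in the plan (assumed).** r, the share of treated patients replaced after stopping in cycle 1 for toxicity or progression and living past it; s, their 6-month OS. Ranges: r from 1% to 8%, s from 20% to 60%. Cycle 1 deaths are taken as counted failures, reading the exception for death as covering both clauses.

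**Step 1: reproduce the design.** P(success | p) = sum over x = 7 to 15 of P(Bin(15, p) = x) × P(Bin(10, p) ≥ 15 − x).
- p = 0.45: 0.0951.
- p = 0.70: 0.9004.

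The design arithmetic is correct, and these properties hold for evaluable patients.

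**Step 2: error for all treated patients.** If all-treated OS is at the null, OS among evaluable patients is (0.45 − r·s)/(1 − r). For r = 0.04 and s = 0.20 this is (0.45 − 0.008)/0.96 = 0.4604. Putting that value into the formula of step 1 gives 0.1142. The full grid, by s:

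| r | 20% | 30% | 45% | 60% |
|---|---|---|---|---|
| 1% | 0.0995 | 0.0977 | 0.0951 | 0.0925 |
| 2% | 0.1041 | 0.1004 | 0.0951 | 0.0899 |
| 4% | 0.1142 | 0.1063 | 0.0951 | 0.0848 |
| 8% | 0.1379 | 0.1194 | 0.0951 | 0.0745 |

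Type I error equals 0.10 at an evaluable rate of 0.4528. That is reached at r = 0.0028/(0.4528 − s): 1.1% for s = 20% and 1.8% for s = 30%.

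**Step 3: can one replacement change a decision?** Yes, if the trial is one survivor short and the replaced patient died before 6 months while the replacement survived. P(6/15) + P(14/25 after passing stage 1):
- p = 0.45: 0.1914 + 0.0817 = 0.273.
- p = 0.60: 0.0612 + 0.1381 = 0.199.
- p = 0.70: 0.0116 + 0.0505 = 0.062.

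At the null most of this is 6/15. Moving to 7/15 only continues the trial, and success then needs at least 8 of 10: 0.1914 × 0.0274 = 0.005. So 0.273 is not the size of the effect; the table in step 2 is.

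**Step 4: effect of counting everyone dosed.** If cycle 1 completers have 70% OS, all-treated OS is (1 − r)·0.70 + r·s. For r = 4% and s = 20% to 30% this is 0.680 to 0.684, with chance of success 0.855 to 0.865. At 1% it is 0.890 to 0.892; at 8%, 0.800 to 0.823. If all-treated OS is itself 70%, power remains 0.900.

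**The case against.** The strongest reply is that an evaluable set is a declared choice in a single-arm activity screen. Sections 9.2 and 9.3 test evaluable patients, and for them type I error is 0.095. That stands. The question is only what the result says about everyone treated.

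Other points that stand in part:
- **The conflict is by implication.** Section 4.3.2 says when patients will be replaced and does not define evaluability for OS; Appendix A concerns response; 4.3.1 ends permissively. A reader might infer a flat contradiction. The text supports poor alignment that needs resolving.
- **Deaths.** A reader might infer that every patient who fails to finish cycle 1 is dropped, deaths included. The closing exception for death probably covers both clauses, so the documents do not establish this.
- **Vital status.** A reader might infer that known outcomes are being thrown away. Section 6.7 starts survival calls at confirmed progression or new anticancer therapy, and calendar footnote k refers to patients off treatment after progression. A toxicity stop with neither has only the general sentence in 4.3. The data are obtainable, not assured.
- **Frequency.** Progression stops in cycle 1 should be few: scheduled imaging comes after 2 cycles (section 3) or every 3 (calendar), and entry requires ECOG 0 or 1 and life expectancy above 3 months. Perforation and hemorrhage stop ramucirumab only.
- **Safeguards.** The Kaplan-Meier estimate has no stated evaluable restriction, all treated patients are evaluable for toxicity, and the lead-in has a stopping rule. These help, but none is the efficacy decision rule.

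**Conclusion.** The point holds at modest size. Section 9.2 removes from both decision counts the patients who stop in cycle 1 for toxicity or progression and live past it, and the replacement rules in 4.3.1 and 4.3.2 do not agree with it. The defect in the text is certain; its size is not. The plan gives neither the rate of such stops nor these patients' survival. The lead-in continues with up to 1 dose limiting toxicity in 6, but that is a tolerance, not an estimate, and not every such toxicity ends the cycle.

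If 4% are replaced and their 6-month OS is 20% to 30%, the chance of declaring activity when all-treated OS is 45% is 0.114 to 0.106, against 0.095 by design and a stated limit of 0.10. It does not change if their OS is 45%, and it falls to 0.085 if their OS is 60%. Much larger inflation needs 10% or more replaced with no survivors, for which the documents give no basis. This should be corrected before analysis, but it does not invalidate the design.

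**What to change.** - **Section 9.2.** Count every patient who received at least one dose in the 7/15 and 15/25 rules, by vital status 6 months after starting on trial, whatever the reason for stopping. State that a death before 6 months, including in cycle 1, is a failure.
- **Replacement for the primary endpoint.** Limit it to patients never dosed, or whose 6-month vital status cannot be obtained because consent to survival follow-up was withdrawn or contact was lost. Report their number and reasons.
- **Sections 4.3.1 (last sentence) and 4.3.2.** Align both with this.
- **Section 6.7 and calendar footnote k.** Start survival follow-up at treatment discontinuation for any reason and run it to at least 6 months from starting on trial. Without this the new count may lack its data.
- **Supportive result.** Report the count in cycle 1 completers.

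The cost is wording changes and a telephone check of vital status for each patient who stops in cycle 1. Fewer patients are replaced, so no extra patients are needed. The counts will include some patients with little exposure, and the chance of success may be slightly lower, as in step 4 of the working.

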4.3.1 Screen Failures/Dropouts/Replacements

A subject who discontinues study participation prematurely for any reasons except death, disease progression and severe toxicity is defined as a dropout.

A subject who, for any reason (e.g., failure to satisfy the selection criteria), terminates the study before the time point used for the definition of "dropout" (see above) is regarded a "screening failure".

Subjects who withdraw from treatment (for any reason) may be replaced.

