*To be given PO on days 1-5 and 8-12 of every 28 day cycle

TAS102 (35mg/m²) twice a day was safely administered with anti-VEGF therapy (bevacizumab)

in a recent a phase 1/2 study⁴⁴. Based on the data, each subject will receive TAS 102 35mg/m² twice a day and ramucirumab 8mg/kg Q2W continuously. Since unexpected toxicities can occur with this combination, we will closely monitor first 6 patients for first 28 days. If none or one of these patients has a dose limiting toxicity, we will continue without dose adjustment. If ≥ 2 patients has a dose limiting toxicity, the dose will be decreased to level -1 (TAS 102: 30mg/m² twice a day and ramucirumab: 8mg/kg Q2W, details in table 1), and 6 additional patients will be enrolled at dose level -1. If none or one of these patients has a dose limiting toxicity at dose level -1 for first 28 days, we will use dose level -1. If ≥ 2 patients has a dose limiting toxicity at dose level -1, the study will be terminated. First 6 or 12 patients depending on dose limiting toxicities will be used for primary and secondary objectives. Dose limiting toxicity is defined as a grade 3 or higher non-hematological toxicity excluding controllable nausea, vomiting, hypertension, diarrhea, transient electrolyte abnormalities and alopecia; grade 4 neutropenia lasting 7 days or more; grade 3 or higher febrile neutropenia; grade 4 thrombocytopenia.

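### Section 9.2 makes patients who cannot complete cycle 1 inevaluable and replaces them, so early treatment failures can leave the 7/15 and 15/25 survival counts, while other sections treat them differently

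*Combined protocol and SAP*

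**What the plan says.** The primary endpoint is survival at 6 months, with death from any cause as the event. Section 9.2 sets two grounds for leaving a patient out. The first is: "Patients will be considered inevaluable for the primary endpoint of 6 months of overall survival if they are not able to complete first cycle". The second applies "if they are lost follow-up prior to 6 months from starting on trial except death". The consequence is firm: "Inevaluable patients will be replaced". Section 9.3 then applies the 15/25 success rule to evaluable patients.

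Other sections set different rules:

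- Section 4.3.1 defines a dropout: "A subject who discontinues study participation prematurely for any reasons except death, disease progression and severe toxicity is defined as a dropout". It also says: "Subjects who withdraw from treatment (for any reason) may be replaced".
- Section 4.3.2 requires dropouts to be replaced and adds: "Patients will be replaced if they come off treatment without any response evaluation for reasons other than drug related AE or disease progression".
- Sections 3 and 5.1 say of the safety run-in: "First 6 or 12 patients depending on dose limiting toxicities will be used for primary and secondary objectives". No exception is made for a run-in patient with a dose limiting toxicity.

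Some stops are mandatory. The footnote to Table 3 (5.1.1.1.1) says that "if grade 4 non-hematotoxicity that is related to the protocol therapy is observed, protocol therapy is to be discontinued". Section 5.1.1.2.3 ends study therapy after a grade 4 pulmonary embolism.

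**The concern.** Survival status does not depend on finishing a treatment cycle, so completing cycle 1 is not needed to observe the endpoint. The patients removed are those whose treatment fails in the first weeks, and they may well survive less long than the others. If so, the success rule is applied to a selected group, and its error rate for all treated patients is no longer the planned one.

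The scope of the exception for death in 9.2 is also unclear. It follows the loss-to-follow-up ground and may or may not reach the cycle-1 ground. Depending on the reading, the bias runs in opposite directions.

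Apart from any bias, the replacement rules disagree. Two analysts who both follow the protocol could count different patients, and with a cut-off of 15 out of 25 one patient can decide the result.

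**Working it through.** **1. One patient under each rule.** Take a patient who stops before finishing the cycle-1 doses because of severe drug-related toxicity, and who is alive at that point.

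| Section | Treatment of this patient |
|---|---|
| 9.2 | Inevaluable; must be replaced |
| 4.3.1, definition | Not a dropout |
| 4.3.1, last sentence | May be replaced |
| 4.3.2 | Outside both groups that must be replaced |
| 3 and 5.1 (if in the first 6 or 12) | Counted for the primary objective |

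A stop for progression gives the same pattern.

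**2. When a stop means non-completion.** TAS 102 is given on days 1–5 and 8–12, and ramucirumab every 2 weeks, so on days 1 and 15. A mandatory stop before day 15 leaves doses ungiven. A stop on days 16–28 can come after every cycle-1 dose, and whether that patient completed the cycle is then open.

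**3. The design as stated.** Inputs from 9.2: 45% against 70% survival, stages of 15 and 10, continue at 7/15, success at 15/25. With p the 6-month survival among counted patients:

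P(success) = Σ (x = 7 to 15) Bin(x; 15, p) × P(Bin(10, p) ≥ 15 − x)

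- p = 0.45: 0.0951 (planned limit 10%)
- p = 0.70: 0.9004 (planned 90%)

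The plan's figures are reproduced.

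**4. Reading A: all cycle-1 non-completers are removed.** Let f be the share of treated patients removed and q their 6-month survival. The documents give neither, so both are assumptions. With 45% survival in all treated patients, survival among those counted is (0.45 − f·q)/(1 − f).

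| f | q | Survival among counted | Type I error |
|---|---|---|---|
| 4% | 45% | 0.4500 | 9.5% |
| 4% | 40% | 0.434/0.96 = 0.4521 | 9.9% |
| 4% | 20% | 0.442/0.96 = 0.4604 | 11.4% |
| 4% | 0% | 0.450/0.96 = 0.4688 | 13.1% |
| 8% | 45% | 0.4500 | 9.5% |
| 8% | 40% | 0.418/0.92 = 0.4543 | 10.3% |
| 8% | 20% | 0.434/0.92 = 0.4717 | 13.8% |
| 8% | 0% | 0.450/0.92 = 0.4891 | 18.0% |

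P(success) reaches 10% when survival among those counted is about 0.4528. Solving q = (0.45 − 0.4528(1 − f))/f gives break-even values of about 38% (f = 4%) and 42% (f = 8%). The stage 1 check weakens too: at f = 8%, q = 20%, the chance of passing it under the null rises from 54.8% to 61.5%.

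**5. Reading B: the exception for death keeps every death before 6 months.** Only survivors among the non-completers are then removed, a share f·q. With 70% survival in all treated patients, survival among those counted is (0.70 − f·q)/(1 − f·q).

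- f = 4%, q = 45%: 0.682/0.982 = 0.6945, power 88.9%
- f = 8%, q = 45%: 0.664/0.964 = 0.6888, power 87.7%

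**6. An intermediate reading.** If the exception reaches only deaths during cycle 1, a patient who stops in cycle 1 and dies later, before month 6, is still removed.

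**7. Is 6-month status available?** Section 4.3 asks patients who discontinue to follow the protocol's survival procedures. Those procedures, in 6.7 and calendar footnote k, are tied to disease progression or, in 6.7, a new anti-cancer therapy. A patient who stops in cycle 1 for toxicity alone has a safety visit about 30 days after the last dose, and no scheduled survival contact until a trigger occurs.

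**The case against.** The best defence is that the intent looks protective. Just before its own rule, 9.2 points to the dropout definitions in 4.3.1, which leave out death, progression and severe toxicity, and 4.3.2 likewise exempts drug-related events and progression. On that view the sections only need harmonising. But 9.2 goes on to state its own inevaluability rule without those exemptions, so the cross-reference does not cure it.

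A second defence is that the design was set for evaluable patients, for whom the type I error is still 9.5%. That is true of the arithmetic. For an all-cause survival endpoint, though, the useful question concerns everyone treated. The Kaplan–Meier estimate in 9.3 is not expressly limited to evaluable patients, but the success decision rests on the count.

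Several points against stronger readings stand:

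- A reader might infer that any mandatory stop in cycle 1 removes the patient. A stop late in the cycle need not, as step 2 shows.
- A reader might infer that existing follow-up already supplies every patient's 6-month status. For a stop without progression or new therapy, 6.7 does not schedule the contact.
- A reader might infer a large inflation, for example 43% if 20% were excluded and all of them died. Nothing in the documents supports such shares. Eligibility requires ECOG 0–1 and life expectancy above 3 months, and no scan is scheduled in cycle 1, so removal for progression would need an unscheduled scan or clinical judgement.

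**Conclusion.** The point holds in a conditional form. Read literally, 9.2 can remove and replace a treated patient whose therapy had to stop in cycle 1, and other sections give that patient a different status. This is an inconsistency in the primary decision rule whatever its numerical effect.

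The size and direction of any bias are not fixed by the documents. Under reading A, the examples with 4% to 8% excluded run from no change (q = 45%) to 11.4% and 13.8% (q = 20%), with 13.1% and 18.0% if none of the excluded survive. The 10% limit is passed only when q is below about 38% or 42%. Under reading B, power falls by about 1 to 2.4 points at q = 45%. It would go too far to say that the trial's type I error does exceed 10%; it can, under stated assumptions. The sample size and cut-offs themselves are correct. The amendment should be made, because it is cheap and affects the trial's main conclusion.

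**What to change.** 1. In 9.2, delete the condition on completing cycle 1. Count in 7/15 and 15/25 every patient who receives at least one dose of either drug, and state that nobody is replaced for toxicity, progression or death.
2. Keep one ground for leaving out a dosed patient: alive when last known, with 6-month vital status not obtainable.
3. Align 4.3.1 and 4.3.2 with this for the primary endpoint, and remove the general permission to replace anyone who withdraws from treatment. Any replacement of run-in patients for the dose limiting toxicity count should be a separate rule that does not affect the survival count.
4. Amend 6.7 and calendar footnote k so that survival contact begins when treatment stops for any reason and covers at least month 6 from starting on trial. Without this, patients stopped for toxicity alone could drift into the exclusion in item 2.

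The cost is a wording amendment and a few extra telephone contacts for patients who stop without progression. Dosing rules, sample size and cut-offs stay as they are. With every dosed patient counted, the 9.5% and 90.0% apply to the treated population, apart from any patients left out under item 2.
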